## 6.4 Statistical analyses

This section describes the primary study analysis. Unless otherwise noted, data from enrolled participants will be analyzed according to the initial randomization assignment regardless of how many vaccinations they received.

Analyses for primary endpoints will be performed using SAS and R. All other descriptive and inferential statistical analyses will be performed using SAS, StatXact, or R statistical software.

No formal multiple-comparison adjustments will be employed for multiple safety endpoints or multiple efficacy endpoints. Multiple comparisons adjustment may be performed for secondary endpoints and objectives, which will be specified in the Statistical Analysis Plan (SAP).

#### 6.4.1 Analysis variables

The analysis variables consist of baseline participant characteristics, safety, efficacy, immunogenicity, and COVID-19 disease, severe COVID-19 and SARS-CoV-2 infection diagnosis variables for the primary and secondary objective analyses.

#### 6.4.2 Baseline comparability

Treatment arms will be compared for baseline participant characteristics using descriptive statistics.

#### 6.4.3 Analysis of relative risk between treatment arms

For the assessment of the coprimary efficacy objectives, this study uses two approaches for determining symptomatic COVID-19 cases, as previously defined in Section 3. For survival data analyses, the time of all participant-level failure and censoring events are reported relative to the time of enrollment (ie, first vaccination) for the pre-Month 6 stage objectives, and relative to the time of Month 6 dose for post-Month 6 stage. For the COVE-based endpoint definition, the time of diagnosis of COVID-19 and severe COVID-19 will be determined by the EAC adjudicators. For the CDC criteria-based definition, the time of diagnosis of lab-confirmed clinical COVID-19 is defined as the minimum date of reported qualifying COVID-19 symptoms and collection date of SARS-CoV-2 positive result (both must occur), and the time of diagnosis of severe COVID-19 to be the minimum date of reported qualifying severe COVID-19 symptoms and collection date of SARS-CoV-2 positive result (both must occur).

The time of diagnosis of the SARS-CoV-2 infection endpoint is the draw time of the first sample with a positive test result by either antibody seroconversion assays or by virus-detection via NAAT. The serology assays are used to ascertain infections occurred anytime during the study among baseline SARS-CoV-2 negative (NAAT and serology negative) participants to address Secondary objectives 1-8. The NAAT are used to ascertain recent or ongoing infections among both baseline SARS-CoV-2 negative and positive participants to address exploratory objectives. The time of diagnosis of the asymptomatic endpoint is the draw time of the first sample with a positive test result by virus detection assays or seroconversion with no reported COVID-19-like illness episodes between enrollment and 14 days after the timepoint at which SARS-CoV-2 infection is ascertained. In case of reinfection of SARS-CoV-2, the first occurrence of a given endpoint is considered.

In the primary and most secondary efficacy analyses, the failure times of participants never observed to be diagnosed with a given clinical endpoint will be right censored at the date of last contact at which endpoint status was assessed or study termination. Participants who report outside COVID-19 vaccines will be censored at the time of receiving such vaccination. Except where otherwise

specified, efficacy analyses of a given endpoint that is counted starting at some specified number of days postvaccination will exclude all participants from the analysis who experienced the particular endpoint diagnosed before the counting period.

The statistical analyses described below use the COVID-19 and severe COVID-19 case definition. Exploratory efficacy analyses may also be considered for a new definition of the endpoints that include suspected but unconfirmed COVID-19 cases.

The primary efficacy analyses focusing on the pre-Month 6 stage will be carried out between the FAS.Grp1 who are SARS-CoV-2 negative at baseline and receive 2 doses of pre-Month 6 vaccination, and FAS.Grp 2 who are SARS-CoV-2 positive at baseline and receive 1 dose of pre-Month 6 vaccination, counting endpoints  $\geq 1$  day post-dose 1. The primary efficacy analyses focusing on the post-Month 6 stage will be carried out between the two different Month 6 arms across all groups, counting endpoints  $\geq 14$  days post the month 6 vaccination. Secondary efficacy analyses will also entail counting endpoints  $\geq 14$  days post the primary vaccination series and endpoints  $\geq 1$  day post the first dose at month 0 in the pre-Month 6 stage, as well as  $\geq 14$  days post the month 6 dose in Groups 1 and 3 combined vs. Groups 2 and 4 combined.

The relative risk (of COVID-19, severe COVID-19, SARS-CoV-2 infection, or SARS-CoV-2 asymptomatic infection) is defined as the incidence rate ratio between the 2 treatment groups in the pre-Month 6 stage or between the 2 treatment arms within a group in the post-Month 6 stage. When there are at least 7 severe COVID-19 endpoints at the primary analysis for a given relative risk assessment, both COVID-19 and severe COVID-19 are used as coprimary endpoints. Otherwise, severe COVID-19 is considered as a secondary endpoint. For the final analyses of the pre-Month 6 objectives, the incidence will be compared across groups by estimating the marginalized cumulative incidence of the endpoint overtime for each group, using a causal inference method that adjusts for potential confounders and accounts for right-censoring of failure times. Under causal assumptions, the marginalized cumulative incidence equals the causal cumulative incidence, interpreted as cumulative incidence if, hypothetically, the entire study population were assigned to the given group under consideration. Sensitivity analyses may also be conducted to account for unobserved confounding factors. For the final analyses of the post-Month 6 objectives, the RR between treatment arms within each group will also be estimated. The causal inference approach used for the pre-Month 6 stage analysis may also be applied for estimating the relative risk of each endpoint for the post-Month 6 dose objectives. More details will be described in the SAP. For analyses before the final analyses, the RR may be estimated from a Poisson regression analysis for both pre- and post-Month 6 stages. To assess potential time effects of vaccine efficacy, the Nelson-Aalen method will be used to plot the estimated cumulative incidence rates over time for the comparison groups. Additional analysis of RR by specified viral

strain categories may also be performed using competing risks failure time methods, as detailed in the SAP.

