***Modifying the final phase of the study based on findings from interim analyses***

Interim analyses of the pre-Month 6 study data have provided new information related to some of the study’s main research questions and have informed modifications to the final phase of the study. Consistent with observations in HIV-negative populations, mRNA-1273 appears safe and well tolerated in PLWH. Reactions after vaccinations were largely mild, with few severe reactions (3%) and no life-threatening or fatal reactions. To date, adverse events in general have been overwhelmingly mild and only one serious adverse event (a case of angioedema) has been considered potentially related to the vaccine. The pre-Month 6 data also suggest that in our study population, participants with hybrid immunity (ie, immunity from both prior infection and vaccination) experienced a reduced incidence of symptomatic SARS-CoV-2 infections compared to participants with only vaccine-induced immunity. Specifically, PLWH and HIV-negative participants who had evidence of prior SARS-CoV-2 infection at baseline and received one dose of mRNA-1273 had an annual COVID-19 incidence rate of 2.2% and 1.5% respectively, compared to 7.1% and 5.8% among such groups without evidence of prior infection at baseline and received two doses of mRNA-1273. This reduction in SARS-CoV-2 incidence could be due to the combination of natural immunity and mRNA-1273 vaccination or due to natural immunity alone. In addition, serious COVID-19 has been very rare in our study population during the pre-Month 6 period, with only 9 cases identified to date, including 7 in PLWH and 2 in people who were HIV-negative. However, asymptomatic SARS-CoV-2 infections were more common than previously appreciated, representing 86% of pre-Month 6 cases. In addition, the data suggest that there are a significant number of likely persistent infections. Of the 1298 (9.3%) participants with at least

one SARS-CoV-2 positive NAAT, 5.6%, 1.8%, and 1.5% were persistently NAAT positive at  $\geq 25$ , 50, 100 days, respectively. Deep genome sequencing of the sequential samples will help determine if these are persistent infections or reinfections (likely both) and what proportion of infections have acquired mutations. The persistent/recurrent infections appear to be more common among the participants without prior SARS-CoV-2 infection, those with active tuberculosis, and PLWH who have low CD4 T-cell counts and/or HIV viremia.

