6. PRE-MONTH 6 & POST-MONTH 6 STAGES : to assess the relative risk of SARS-CoV-2 infection defined by nucleocapsid protein seroconversion regardless of symptomology after the Month 6 dose in Group 1 (PLWH who are SARS-CoV-2 negative at baseline) and in Group 3 (people HIV-negative who are SARS-CoV-2 negative at baseline) combined, among those who received mRNA-1273 at Month 6 vs. those who received mRNA-1273.222 at Month 6, counting endpoints starting 1 day after dose 1, 14 days after the last pre-Month 6 dose , or 14 days after Month 6 dose until the end of follow up.	SARS-CoV-2 infection diagnosed by seroconversion throughout the study.

Secondary Objectives	Secondary Endpoints
7. PRE-MONTH 6 & POST-MONTH 6 STAGES: to assess the relative risk of asymptomatic SARS-CoV-2 infection defined by nucleocapsid protein seroconversion after the Month 6 dose in Group 1 (PLWH who are SARS-CoV-2 negative at baseline) and in Group 3 (people HIV-negative who are SARS-CoV-2 negative at baseline) combined, among those who received mRNA-1273 at Month 6 vs. those who received mRNA-1273.222 at Month 6, counting endpoints starting 1 day after dose 1, 14 days after the last dose before Month 6 dose, or 14 days after Month 6 dose until the end of follow up.	SARS-CoV-2 infection diagnosed by seroconversion in the absence of symptoms.
8. PRE-MONTH 6 & POST-MONTH 6 STAGES: to assess the relative risk of symptomatic COVID-19, and severe COVID-19 after the Month 6 dose in Groups 1 and 3 together (participants who are SARS-CoV-2 negative at baseline regardless of HIV status) and in Groups 2 and 4 together (participants who are SARS-CoV-2 positive at baseline regardless of HIV status), respectively, among those who received mRNA-1273 at Month 6 vs. those who received mRNA-1273.222 at Month 6, counting endpoints starting 1 day after dose 1 or 14 days after the last dose before Month 6 dose until the end of follow up.	COVID-19 and severe COVID-19 as defined above
9. To assess post-vaccination immune response markers and immune markers as correlates of risk of COVID-19 and as correlates of protection against COVID-19 in all study groups together.	SARS-CoV-2-specific neutralization antibody, binding antibody and cellular immune responses

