## 9.5 Active COVID-19 symptomatic surveillance

Participants will use Memory Aid 1 for surveillance of symptoms and be instructed to contact the clinic if they have COVID-19 like symptoms. Additionally, the site will make arrangements to contact the participant to elicit symptoms of COVID-19 as described below. These symptoms will be used to establish whether a participant meets criteria for COVID-19 disease as defined by Primary Endpoint 1. If a participant has symptoms consistent with COVID-19, they will be instructed to contact the clinic to review their symptoms and if needed to schedule a COVID-19 Symptom visit. Results of testing will be reported through the CRF and participants who have a positive SARS-CoV-2 NAAT test result will follow procedures described in Section 9.6 and [Appendix J](#).

The below prespecified symptoms that meet the criteria for suspicion of COVID-19 will be elicited approximately every 2 weeks from the participant and the presence of any one of these symptoms lasting at least 48 hours (except for fever and/or respiratory symptoms) will result in the site arranging a Symptom Visit to collect a nasal swab within 72 hours. (If the site becomes aware of the symptoms >72 hours after they have resolved, nasal swab/symptom visit is not required.)

[figure not shown]
- Fever (temperature  $\geq 38^{\circ}\text{C}$ ) or chills (of any duration, including  $\leq 48$  hours)
- Shortness of breath or difficulty breathing (of any duration, including  $\leq 48$  hours)
- Cough (of any duration, including  $\leq 48$  hours)
- Fatigue
- Muscle or body aches
- Headache
- New loss of taste or smell (of any duration, including  $\leq 48$  hours)
- Sore throat

- Congestion or runny nose
- Nausea or vomiting
- Diarrhea

It is important to note that some of the symptoms of COVID-19 overlap with systemic adverse reactions that are expected after vaccination with mRNA-1273 and mRNA-1273.222 vaccines (eg, myalgia, headache, fever, chills). During the first 7 days after vaccination, when these adverse reactions are common, investigators should use their clinical judgement to decide if a COVID-19 symptom visit should be scheduled. Any study participant reporting respiratory symptoms during the 7-day period after vaccination should be evaluated for COVID-19.

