6.3.2 Asymptomatic/subclinical SARS-CoV-2 infection

TBD.

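### As written, any COVID-19-like illness reported since enrolment disqualifies a later infection from the asymptomatic endpoint, so that endpoint would be undercounted, increasingly after Month 6

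*Protocol*

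**What the plan says.** - **Definition.** Protocol 6.4.3 dates the asymptomatic endpoint at "the first sample with a positive test result by virus detection assays or seroconversion", on condition that there were "no reported COVID-19-like illness episodes between enrollment and 14 days after the timepoint at which SARS-CoV-2 infection is ascertained". It does not define an illness episode.
- **Objective.** Secondary objective 7 (Protocol 3) is "to assess the relative risk of asymptomatic SARS-CoV-2 infection defined by nucleocapsid protein seroconversion after the Month 6 dose" in Groups 1 and 3 combined, comparing the two Month 6 vaccines. Its endpoint is "SARS-CoV-2 infection diagnosed by seroconversion in the absence of symptoms", with no symptom window and no mention of NAAT. Besides a period starting 1 day after dose 1, its counting periods start "14 days after the last dose before Month 6 dose, or 14 days after Month 6 dose until the end of follow up".
- **Risk set.** Protocol 6.4.3 removes a participant before the counting period only for an earlier occurrence of the same endpoint, not for an earlier illness.
- **Symptom enquiry.** Protocol 9.5: "The below prespecified symptoms that meet the criteria for suspicion of COVID-19 will be elicited approximately every 2 weeks from the participant". The list includes headache, fatigue, runny nose, cough and diarrhoea.
- **SAP.** Section 6.3.2, "Asymptomatic/subclinical SARS-CoV-2 infection", is marked only as still to be determined, and the opening of Section 6 leaves the definition to later SAP versions. Protocol 6.4.3 is therefore the only rule in force.

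**The concern.** A symptom-free condition should ask whether the infection itself came with symptoms. This one asks whether the participant has had any COVID-19-like illness since joining a study that lasts up to 18 months.

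Take a participant with a NAAT-negative cold in Month 2, a negative Month 6 serology draw and an infection without symptoms at Month 10. The cold cannot be that infection, yet it disqualifies it. The participant goes on contributing follow-up but can never become a case. If the Month 10 infection is found by swab, it is not symptomatic either, because the CDC-derived definition needs a symptom within 14 days of the positive NAAT.

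The chance of having had at least one such illness only rises with time. The loss is therefore largest after Month 6, where the two vaccines are compared. Protocol 2.1 says monthly swabs were added to find asymptomatic infections better, and reports that "asymptomatic SARS-CoV-2 infections were more common than previously appreciated, representing 86% of pre-Month 6 cases". A definition that drops a growing share of them works against that aim.

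**Working it through.** The documents give no event count, power or illness rate for objective 7, so there is no figure to reproduce. What follows is an illustration.

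**Inputs**
- Visit days from the protocol schedule: Month 6 = Day 169, Month 12 = Day 365, Month 18 = Day 547.
- 14 days after ascertainment, from Protocol 6.4.3.
- Serology at Months 0 and 6: SAP Section 5 expects central serology from all participants at both. A further draw at Month 12 is assumed here.
- **Assumption:** unrelated COVID-19-like illness is reported at a constant rate r of 0.25 to 1.5 episodes per person-year, independent of infection.

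**Formula.** Share of truly asymptomatic infections that still qualify = exp(−r × window days / 365.25).

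| Window | Days | r = 0.25 | r = 1.5 |
|---|---|---|---|
| Current rule, ascertained Month 6 | 169 + 14 = 183 | 88% | 47% |
| Current rule, Month 12 | 365 + 14 = 379 | 77% | 21% |
| Current rule, Month 18 | 547 + 14 = 561 | 68% | 10% |
| Month 0 draw to Month 6 draw | 169 − 1 = 168 | 89% | 50% |
| Month 6 draw to Month 12 draw | 365 − 169 = 196 | 87% | 45% |
| Same, plus 14 days after the positive draw | 196 + 14 = 210 | 87% | 42% |
| 14 days either side of a positive NAAT | 28 | 98% | 89% |

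Example: Month 12 at r = 0.25 gives exp(−0.25 × 379 / 365.25) = exp(−0.259) = 77%.

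**Reading the table**
- For a Month 6 seroconversion whose last negative draw is baseline, anchoring to that draw changes almost nothing: 168 + 14 = 182 days against 183.
- For a Month 12 seroconversion after a negative Month 6 draw, the gain is moderate. Any draw in between would shorten the interval and increase it.
- The large gain belongs to NAAT-detected infections only.

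**Cost in power.** With 1:1 allocation, power = Φ(½ √D × ln RR − 1.96). At r = 0.5 the current rule keeps exp(−0.5 × 379 / 365.25) = 60% at Month 12. For an illustrative 100 events falling to 60, power at a relative risk of 2.0 falls from Φ(3.47 − 1.96) = 93% to Φ(2.68 − 1.96) = 77%.

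**Bias.** Equal illness rates in the two arms multiply both counts by the same factor, so the relative risk is unchanged. The arms can differ only after the Month 6 dose. The differential route is COVID-19 that one vaccine prevents better. The highest annual incidence in Protocol 2.1 is 7.1%. If one arm halved it, the rate difference would be 0.0355 per year, and a full year would shift the ratio by exp(0.0355) = 1.04.

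**The case against.** **A long look-back is partly necessary.** Objective 7 is defined by seroconversion, which dates an infection only to between the last negative and first positive draw. When baseline is the last negative draw, looking back to enrolment is correct. This stands. The fault is that the window does not stop at a later negative sample, and that it counts illnesses that tested negative.

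**NAAT may not belong to this objective.** Elsewhere in 6.4.3 serology is assigned to secondary objectives 1–8 and NAAT to exploratory ones. A reader might infer that the 98% to 89% figure describes objective 7 as a whole. It does not: it applies only if NAAT-detected infections count, which Sections 3 and 6.4.3 answer differently.

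**The size is assumed.** The episode is undefined, and under Protocol 9.5 most non-respiratory symptoms other than fever, chills or loss of taste or smell must last at least 48 hours to prompt a visit. If the present rule produced the 86% asymptomatic share, at most 14% of pre-Month 6 cases could have been removed. The protocol does not say which definition lies behind that share, and it covers only the stage where the loss is smallest, so it settles nothing about later follow-up.

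**No infection is lost to the study.** Secondary objective 6 counts infection regardless of symptoms. A reader might also expect symptomatic and asymptomatic counts to sum to all infections. They would not under any window, since symptomatic cases need a NAAT and objective 7 uses seroconversion in two groups only.

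**Conclusion.** The concern holds as a fault in the written definition. Followed literally, it undercounts asymptomatic infection, and more so the later the infection. The direction follows from the text; the size rests on the assumed illness rate and its independence from infection. At 0.25 to 1.5 episodes per year, 77% to 21% of truly asymptomatic Month 12 infections qualify now. With a look-back only to a negative Month 6 draw it is 87% to 45% (87% to 42% with 14 days added). The change is negligible for a Month 6 seroconversion last negative at baseline.

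Two stronger readings are not supported. One is that the trial has already miscounted this endpoint: the SAP has not yet specified the analysis. The other is that the vaccine comparison is materially biased: objective 7 compares randomised arms, unrelated illness should balance, and the differential route gives a factor of about 1.04 on the protocol's own highest incidence. Lost events and power in one secondary endpoint are the main harm. No primary analysis is affected.

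**What to change.** Amend Protocol 6.4.3 and write the same text into SAP 6.3.2:

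1. For seroconversion, run the symptom-free window from the last negative serology draw to 14 days after the first positive draw.
2. For NAAT-detected infection, run it from 14 days before to 14 days after the first positive swab.
3. Define the illness episode, and do not count episodes that tested NAAT-negative.
4. Reconcile Protocol 3 (seroconversion only) with 6.4.3 (virus detection or seroconversion) on which tests count for objective 7.
5. Keep the look-back to enrolment as a sensitivity analysis.

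The cost is a few sentences. The plan already collects symptom reports, swab results and serology draws with dates, so no visit or sample is added. The downside is that a few infections with symptoms outside the window, or with a falsely negative swab, may be classed as asymptomatic; the sensitivity analysis shows how much that matters.

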#### 6.4.4 Safety/Tolerability analysis

Safety endpoints will be assessed in the FAS cohort. Since enrollment is concurrent with receiving the first injection, all participants will have received at least 1 vaccination and therefore will provide some safety data.

During the course of the trial, analyses of safety data will be prepared for review by the DSMB at a frequency determined by the DSMB for as long as it is involved in the trial. Ad hoc safety reports may also be prepared for DSMB review at the request of the PSRT. The OG must approve any other requests for safety data prior to the end of the scheduled follow-up visits.

##### 6.4.4.1 AEs and SAEs

AEs will be summarized using MedDRA System Organ Class and preferred terms. Tables will show by treatment group the number and percentage of participants experiencing an AE within a System Organ Class or within preferred-term category by severity and by relationship to study product. For the calculations in these tables, a participant with multiple AEs within a category will be counted once under the maximum severity and by causal relationship to study product. Formal statistical testing comparing arms is not planned for all AEs since interpretation of differences must rely heavily upon clinical judgment. Barnard's tests will be used to compare rates of SAEs deemed related to study products between vaccine arms. The false discovery rate procedure of Mehrotra and Heyse (155) may be applied to compare grouped systemic SAEs divided by body systems between treatment arms.

A listing of SAEs will provide details of the events including severity, relationship to study product, time between onset and last vaccination, and number of vaccinations received. A separate listing will do the same for AESIs. AESIs for this protocol include but are not limited to potential immune-mediated disorders.

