### 6.3.1 Power calculations for coprimary objectives 1-4 (Efficacy)

Let  $VE(COVID)$  and  $VE(Severe\ COVID)$  denote vaccine efficacy of the vaccine regimen vs. counterfactual placebo among baseline SARS-CoV-2 negative participants against COVID-19 and severe COVID-19, respectively. The relative risk objectives are assessed in terms of cumulative incidence ratios between the active vaccine regimens without analysis of counterfactual placebo arms; the notations  $VE(COVID)$  and  $VE(Severe\ COVID)$  are mainly used for purposes of communicating effect sizes.

The following calculations focus on the COVID-19 endpoint because the severe COVID-19 endpoint could potentially be changed to be a secondary endpoint if there are insufficient severe COVID endpoints (Section 6.4.3). For the assessment of pre-Month 6 stage objectives, sample sizes of Groups 1 and 2 in the FAS are considered. For the assessment of post-Month 6 stage objectives, the following calculations consider approximately 4000 participants in Groups 1-4 received their Month 6 vaccination (mRNA-1273 vs. mRNA-1273.222) per randomization under protocol version 6. This sample size is consistent with study data as of June 2023. As shown in the upper portion (pre-Month 6 stage) of Table 6-2, there is ample power ( $> 90\%$ ) to detect a relative risk of 2.0 between Groups 1 and 2 against the null hypothesis  $H_0: RR = 1.0$  during Month 0 and 6 in the pre-Month 6 stage. In reality, the sample sizes of the PLWH hybrid immunity group who receive 1 pre-Month 6 dose and the PLWH pure vaccine group who receive 2 pre-Month 6 doses are likely smaller than the sample sizes of Groups 1 and 2, respectively. As shown in the lower portion (post-Month 6 stage) of Table 6-2, when the annual incidence of the primary endpoint is in the range of 2.5%- 3.5% in the mRNA-1273 arm, there is approximately 80-90% power to detect a relative risk of 2.0 – 2.5 between mRNA-1273 vs. mRNA-1273.222 vaccination during Month 6.5 and 18 in the post-Month 6 stage.

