## 6.8 Randomization implementation

The randomization sequence will be computer generated and provided by the data monitoring center (DMC) to each CRS, ideally through a Web-based randomization system. For statistical efficiency and to avoid chance imbalance in exposure or prognostic factors between treatment groups, the randomization will be stratified by study site, HIV-1 infection status, and SARS-CoV-2 serostatus at enrollment. The randomization will be done in blocks to ensure balance between the vaccine arms within levels jointly determined by these factors. The block size

ensures balance among treatment arms over different epidemiological stages of the pandemic. At each institution, the pharmacist with primary responsibility for dispensing study products is charged with maintaining security of the treatment assignments.

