The Ubuntu study enrolled a total of 14,237 participants into 4 study groups based on their baseline HIV serostatus (positive or negative) and anti-spoke SARS-CoV-2 Point-of-Care serology (POCS) status (positive or negative). Prior to protocol version 6.0, for Part A of the study, participants were assigned to receive 1 dose (Month 0), or 2 doses (Month 0 and Month 1) of mRNA-1273 based on their baseline POCS result being positive or negative, respectively. Prior to protocol version 6.0, for Part B of the study, randomization code was generated but all participants received the monovalent mRNA-1273 vaccine at Month 6 due to the bivalent vaccine not being available at the time, and no randomization assignment was actually performed. At the time of implementation of protocol version 6.0 after the bivalent vaccine became available, The Ubuntu study enrolled a total of 14,237 participants into 4 study groups based on their baseline HIV serostatus (positive or negative) and anti-spoke SARS-CoV-2 Point-of-Care serology (POCS) status (positive or negative). Prior to protocol version 6.0, for Part A of the study, participants were assigned to receive 1 dose (Month 0), or 2 doses (Month 0 and Month 1) of mRNA-1273 based on their baseline POCS result being positive or negative, respectively. Prior to protocol version 6.0, for Part B of the study, randomization code was generated but all participants received the monovalent mRNA-1273 vaccine at Month 6 due to the bivalent vaccine not being available at the time, and no randomization assignment was actually performed. At the time of implementation of protocol version 6.0 after the bivalent mRNA-1273.222 vaccine became available, the previous randomization code was replaced with the randomization code generated under an updated randomization plan, ensuring that the treatment number assigned at original “randomization” was kept and corresponded to either mRNA-1273 or mRNA-1273.222. This allowed the site to use the randomized assignment to define the Month 6 vaccination for participants receiving the Month 6 vaccination under protocol version 6.0. An updated treatment key was provided to sites with participants who re-consented on protocol version 6.0, for documenting the Month 6 vaccinations only. Only as many treatment assignments as

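### The one between-arm safety test the protocol commits to is on related SAEs, where about 0.3 events are expected after Month 6, so a non-significant result would say almost nothing

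*Protocol*

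**What the plan says.** Protocol section 3 makes safety and tolerability of both vaccines, in both stages, primary objective 5. SAEs and AESIs are collected in everyone throughout; solicited and unsolicited AEs are collected in a subset.

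Section 6.4.4.1 sets out the between-arm analysis:

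- Barnard's "tests will be used to compare rates of SAEs deemed related to study products between vaccine arms". This is the only safety test stated as definite.
- "Formal statistical testing comparing arms is not planned for all AEs", because differences are to be interpreted clinically.
- A false discovery rate procedure "may be applied to compare grouped systemic SAEs divided by body systems between treatment arms". This is optional.
- In the AE tables, "a participant with multiple AEs within a category will be counted once under the maximum severity". No dose or stage window is given for these tables.

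The arms are the randomised ones: section 6.8 says "The randomization will be done in blocks to ensure balance between the vaccine arms within levels jointly determined by these factors". Table 1-1 shows that the A and B arms of each group differ only in the Month 6 product. The SAP supplied covers COVID-19 and severe COVID-19 risk and has no safety section.

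**The concern.** A formal test invites a reader to take its result as the answer. Here it is applied to the rarest safety outcome in the trial. The protocol reports that, in the interim pre-Month 6 data, "only one serious adverse event (a case of angioedema) has been considered potentially related to the vaccine". If related SAEs are about as rare after Month 6, the test will almost certainly be non-significant whether or not the 100 mcg bivalent dose carries a moderate excess. That result could then be read as evidence of similar safety.

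The outcome also depends on a judgement of relatedness. Randomisation at Month 6 permits a comparison that needs no such judgement, using SAEs and AESIs already recorded for every participant, but no overall comparison of these between arms is committed to.

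**Working it through.** **The plan's own precision figure.** Section 6.3.2 gives zero-event upper 95% limits of 0.02% (N = 15,600) and 0.2% (N = 1,500). The two-sided Clopper-Pearson limit is 1 − 0.025^(1/N), giving 0.024% and 0.246%. Both round to the stated values, so the figure reproduces.

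**Inputs.**
- Related SAEs to date: 1 (Protocol 2.1, interim analyses).
- Denominator: the same text gives 1298 participants as 9.3%, so 1298/0.093 = 13,957. The SAP gives 14,237 enrolled.
- Month 6 cohort: Protocol 6.3.1 works with "approximately 4000 participants in Groups 1-4 received their Month 6 vaccination" under randomisation; Table 6-2 splits them 2,000 vs 2,000.
- Alpha: not stated for Barnard's test. Two-sided 0.05 is assumed, as in the efficacy power calculation.

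**Expected related SAEs, both arms, at an equal rate.** 4000/13,957 = 0.29; with 14,237 it is 0.28. The exact Poisson interval for one event is 0.025 to 5.57, so the range is 0.025 × 4000/13,957 = 0.01 to 5.57 × 4000/13,957 = 1.6. Counting per dose, and assuming 25% to 50% of participants had two earlier doses, it is 4000/(13,957 × 1.25) = 0.23 to 4000/(13,957 × 1.5) = 0.19.

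**What the test needs at 2,000 per arm.** This is the exact unconditional test with pooled score statistic, maximised over the common rate; two implementations were used.

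| Split | Two-sided p |
|---|---|
| 3-0 | 0.085 to 0.097 |
| 4-0 | 0.046 to 0.047 |
| 5-0 | 0.025 to 0.026 |

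The smallest significant result is 4-0. With 0.29 expected, the Poisson probability of four or more events in total is 0.0002.

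**Power, with the monovalent rate at 1/13,957.**

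| Rate ratio | 2,000 per arm | 6,240 per arm (Table 6-4) |
|---|---|---|
| 2 | 0.02% | 0.9% |
| 5 | 0.5% | 12% |
| 10 | 5% | 47% |
| 20 | 28% | 89% |
| 40 | 76% | >99% |

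The 6,240 assumes 80% of 15,600 receive a Month 6 dose under the current version. That conflicts with the roughly 4,000 in 6.3.1. The zero-event upper limit is 1 − 0.025^(1/2000) = 0.18% rather than 1 − 0.025^(1/6240) = 0.06%.

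At the upper limit of the rate (5.57/13,957 = 0.04%), the same enumeration at 2,000 per arm gives power of 4% for a rate ratio of 2 and 30% for 5.

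**All SAEs instead, 2,000 per arm.** The documents give no SAE rate, so a range is assumed. Power is by binomial enumeration of the pooled Z test at two-sided 0.05; the half-width is 1.96 × √(2p(1 − p)/2000).

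| Assumed monovalent SAE risk p | Power, RR 1.5 | Power, RR 2 | 95% CI half-width for the risk difference (equal risks) |
|---|---|---|---|
| 1% | 29% | 75% | 0.62 points |
| 2% | 53% | 96% | 0.87 points |
| 3% | 71% | >99% | 1.06 points |
| 5% | 91% | >99% | 1.35 points |

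**The AE-table window (illustration only).** Suppose the tables were cumulative, the per-dose risk were 3% and independent between doses, and it doubled to 6% at Month 6 with the bivalent vaccine. Groups 1 and 3 would show 1 − 0.97² × 0.94 = 11.6% vs 1 − 0.97³ = 8.7% (ratio 1.3). Groups 2 and 4 would show 1 − 0.97 × 0.94 = 8.8% vs 1 − 0.97² = 5.9% (ratio 1.5). The true Month 6 ratio is 2.

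**The case against.** **Objective 5 is to assess safety, not to test a difference.** The plan sizes it by confidence intervals and explains why broad AE testing is not planned. This is fair, and it is why the fix asks for estimates with intervals and only a nominal p-value. It does not rescue the one test that was chosen, and the Table 6-4 intervals are for single arms, not contrasts.

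**A reader might infer that a bivalent safety difference cannot be seen at all.** The documents do not support that. They provide by-arm AE tables, SAE listings with time since last dose and number of doses, AESI listings, reactogenicity after each dose, 28-day AEs, a sentinel review of about 120 Month 6 recipients and prompt review of related SAEs. In the Safety Subset at Table 6-4's 600 per arm, a nominal comparison of 3% vs 6% has 71% power. If the subset shrinks in proportion (1,500 × 4000/15,600/2 = 192 per arm, an assumption), it has 29%.

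**A reader might also infer that AE tables count each participant once over all doses.** The text says once within a category and is silent on the window. Dose- and stage-specific collection elsewhere makes by-dose tables quite possible. This is missing detail, not a demonstrated error.

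**The denominators could be larger.** Safety cohorts are analysed by treatment received, which could add monovalent recipients vaccinated before version 6.0. With an assumed 4,000 to 10,000 monovalent recipients, a 2-0 split in the bivalent arm gives p of 0.045 to 0.009; at 6,000, power for a tenfold rate is at least 27%. That is true, but the comparison is then not randomised, and power remains low.

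**All SAEs and AESIs mix in efficacy.** Appendix O reports COVID-19 events that meet SAE criteria, and its AESI list includes ARDS and anosmia. Better bivalent protection could offset a safety excess. This stands, and the fix allows for it.

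**Blinding.** The SAP says participants were blinded and that "An updated treatment key was provided to sites with participants who re-consented on protocol version 6.0". It would be wrong to conclude that those judging relatedness knew the assignment: a separate blinding management plan exists but was not supplied, and the protocol places assignment security with the pharmacist.

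**Conclusion.** The point holds for the committed test. About 0.3 related SAEs (0.01 to 1.6) are expected among some 4,000 randomised Month 6 recipients, while significance needs at least four, all in one arm. Power is about 5% for a tenfold rate, and reaching 80% would take a rate ratio between 40 (76%) and 50 (88%). A non-significant result should not be read as evidence of similar safety.

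This rests on carrying one pre-Month 6 event forward to Month 6, on 2,000 per arm, and on two-sided 0.05. Even the upper end of the range leaves power at 4% for a doubling.

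It does not follow that the trial is blind to a safety difference, or that such a difference would be reported as absent; the other safety data are available descriptively. The unstated AE-table window calls for clarification only. Safety specifications may also exist in documents not supplied. This is an inexpensive improvement to a primary objective, not a flaw that invalidates it.

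**What to change.** In Protocol 6.4.4.1:

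1. Compare all SAEs, and separately all AESIs, with onset after the Month 6 dose, regardless of attribution, between the arms in participants randomised at Month 6. Report risk differences with 95% confidence intervals, and label the Barnard p-value as nominal.
2. Show each comparison with and without COVID-19 events, because these are efficacy outcomes.
3. Keep related SAEs as a supporting row, with the expected count stated so that a null result is not over-read.
4. As a clarification, state that the Month 6 AE tables by arm include only events after the Month 6 dose, since both arms received identical vaccine before it.

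The cost is a few sentences and a few extra tables from data already collected. The downside is that all-cause SAEs include background illness, which adds noise and dilutes a relative effect; at an assumed 1% risk, power for a rate ratio of 1.5 is still only 29%. The intervals will at least show what has and has not been excluded.
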